6.12.2 Assessment of Breakthrough Angioedema Attacks

If a breakthrough attack occurs, subjects (or caregivers) should assess and record the following information in the study diary:

- Presence of pain or swelling at each anatomic location (ie, upper airway [laryngeal], gastrointestinal/abdominal, facial, genitourinary, and extremity/peripheral) by indicating the overall severity (ie, mild, moderate, or severe [as defined below])
- Overall amount of pain associated with the breakthrough attack using a VAS (only for subjects at least 5 years of age)
- Any triggers associated with the attack
- Any health care visit for the attack (investigational site, clinic or hospital/emergency department)
- Any medications received to manage attack symptoms
- Duration of symptoms (ie, time symptoms start to improve and time symptoms completely resolve)

In addition to the subject's self-assessment, the Investigator should assess and record the overall severity of the attack if the subject seeks treatment for symptoms at the site.

Treatment with CINRYZE

The Investigator (or qualified delegate) or subject (trained and deemed independent) may administer a supplemental dose of CINRYZE to treat the breakthrough attack. Subjects self-administering CINRYZE will record clinical assessments associated with breakthrough attacks in the study diary.

Following the administration of CINRYZE, subjects (or caregivers) will record their symptoms (the presence of pain or swelling at each anatomic location) and assess the overall severity of the breakthrough attack every 15 minutes for up to 4 hours post-infusion using the following scale:

- No symptoms.
- Mild: The attack symptoms are noticeable but are easily tolerated by the subject and do not interfere with the subject's daily activities.
- Moderate: The attack symptoms interfere with the subject's ability to attend work/school or participate in family life and social/recreational activities).
- Severe: The attack symptoms significantly limit the subject's ability to attend work/school or participate in family life and social/recreational activities.

Subjects (or caregivers) also will rate the overall amount of pain associated with the

Protocol 0624-209 with Amendments 1, 2, 3, CINRYZE (C1 inhibitor [human])

breakthrough attack using a VAS (for subjects at least 5 years of age) on the same schedule as overall attack severity.

In addition to the subject's self-assessment, the Investigator should assess and record the overall severity every 15 minutes for up to 4 hours post-infusion if the subject seeks treatment at the site.

NOTE: If a subject has adequately responded to treatment with CINRYZE, the subject may omit further assessments up to 4 hours post-infusion (and if applicable, be discharged from the investigational site) provided that overall attack severity has been assessed for at least 1 hour.

Subject diary data will be used by study personnel to record the onset date and time of the breakthrough attack, as well as the date and time of onset of symptom improvement and Complete Resolution (defined in Section 7.6.2) in the CRF.

6.13 Quality of Life

6.13.1 Angioedema Quality of Life (AE-QoL) Questionnaire

The Angioedema Quality of Life (AE-QoL) is a questionnaire on the quality of life of patients suffering from recurrent angioedema. It consists of 17 specific questions that are associated with work, physical activity, free time, social relations, and diet. Subjects will be asked by study personnel how often they were restricted by—as well as the difficulties and problems that could be associated with—recurrent swellings (angioedema) during the previous 4 weeks. The AE-QoL questionnaire will be completed at the time points specified in Schedule 1 and Schedule 3. This instrument will be administered as appropriate for each subject's age (ie, includes option of guidance from parent/guardian).

6.14 Self-administration Survey

A self-administration survey containing questions for subjects (or caregivers) and the Investigator's assessment of the overall experience with self-administration of IV CINRYZE will be completed on Visit 24.

Subjects (or caregivers) who have self-administered treatment during the study, will be asked specific questions regarding training materials and oversight by the Investigator or qualified delegate, ease of reconstituting and self-administering CINRYZE, any challenges or obstacles encountered, and to rate their overall satisfaction with self-administered treatment. The Investigator or qualified delegate will provide their overall assessment of the training process and the success/challenges of teaching subject (or caregiver) self-administration skills. Study personnel will enter the survey responses in the CRF.

6.15 Discontinuation of Subjects

A subject may withdraw from the study at any time for any reason without prejudice to their future medical care by the physician or at the institution. The Investigator or Sponsor may withdraw the subject at any time (eg, in the interest of subject safety). The Investigator is encouraged to discuss the withdrawal of a subject from investigational product with the Medical Monitor when possible.

If investigational product is discontinued, regardless of the reason, the Early Discontinuation Visit procedures listed in Schedule 3 are to be performed as completely as possible. Whenever possible, all discontinued subjects should also complete the 1-Week and 1-Month Post-treatment Follow-up Visits. Comments (spontaneous or elicited) or complaints made by the subject must be recorded in the source documents. The reason for termination and the date of stopping investigational product must be recorded in the CRF and source documents.

If subjects withdraw or discontinue after enrollment, additional subjects may be enrolled to ensure at least 6 subjects complete the study.

For those subjects who discontinue before receiving study drug, demographic information, inclusion/exclusion information, and the reason for not receiving study drug will be recorded in the CRF. No additional study procedures or follow-up will be performed on subjects who discontinue before receiving study drug.

6.15.1 Reasons for Discontinuation

The reason for withdrawal must be determined by the Investigator and recorded in the subject's medical record and on the CRF. If a subject is withdrawn for more than 1 reason, each reason should be documented in the source document and the most clinically relevant reason should be entered on the CRF.

Reasons for discontinuation include but are not limited to:

- Adverse event
- Protocol violation
- Withdrawal by subject
- Lost to follow-up
- Lack of efficacy
- Other [specify reason on the CRF].

Subjects who discontinue study drug due to an AE will be followed until the event is either resolved or assessed as stable by the Investigator.

A subject will be considered lost to follow-up after 3 documented attempts are made, including at least one attempt via written communication.

7 STATISTICAL METHODOLOGY

7.1 Sample Size

A sufficient number of subjects will be enrolled to ensure that a minimum of 6 subjects complete the study. When 6 subjects have completed the 12-week treatment period, no further subjects will be enrolled; however, all subjects already enrolled in the study will be followed to study completion.

7.2 Populations

All treated subjects (ie, Intent-to-Treat Safety [ITT-S] Population: subjects who receive any amount of study drug) will be included in the safety analyses. All subjects with evaluable PK/PD profiles (ie, PK/PD Population) will be included in PK/PD analyses as appropriate.

7.3 Statistical Methods

Data will be summarized using the same methods that were used in the overseas development program for IV CINRYZE. Experimental results will be summarized using descriptive statistics according to data type (n, mean, standard deviation or standard error, median, and range for continuous endpoints; number and percent of subjects in each category for categorical endpoints). To establish context, efficacy/pharmacology results from this study may be superimposed (eg, graphically) on experimental data from previous overseas studies, as appropriate.

7.4 Safety Analyses

The following will be assessed:

- Adverse events (including treatment-emergent adverse events).
- Summary statistics and changes from baseline to post-baseline for laboratory testing, vital signs, and, if applicable, any ECG findings will be presented.
- Results of C1 INH antibody testing will be reported for individual subjects and summarized as appropriate.

NOTE: Treatment-emergent events include all adverse events that start during the treatment period (and up to 7 days after the last dose of investigational product) and were not seen at baseline, or were seen at baseline but worsened in frequency and/or severity during the treatment period (and up to 7 days after the last dose of investigational product).

7.5 Pharmacokinetic and Pharmacodynamic Analyses

Concentrations of C1 INH antigen (protein volume), functional C1 INH activity (potency), and complement C4 and C1q for individual subjects will be determined. Results will be summarized using descriptive statistics at each time point with and without baseline correction. C1q concentrations will be assessed at baseline only (ie, pre-infusion, Dosing Visit 1).

Protocol 0624-209 with Amendments 1, 2, 3, 4 CINRYZE (C1 inhibitor [human])

Pharmacokinetic/pharmacodynamic parameters will be calculated using observed and baseline-corrected concentration-versus-time data using non-compartmental techniques. Pharmacokinetic/pharmacodynamic parameters to be determined include C_{max} and its time of occurrence (t_{max}) , minimum observed concentration (C_{min}) , average concentration at steady state (C_{avg}) , area under the plasma concentration versus time curve from time 0 to selected time point $(AUC_{0-\tau})$, elimination rate constant (K_{el}) , terminal elimination half-life $(t_{1/2})$, volume of distribution (V_Z) , and plasma clearance (CL), as appropriate. Terminal elimination half-life will be estimated by log-linear regression and will use at least three time points. Other non-compartmental PK/PD parameter values also may be calculated. Non-compartmental PK/PD analyses will be performed using commercially available software (Phoenix® WinNonlin®, version 6.3 or higher; Pharsight, a Certara company).

If warranted, an exploratory PK/PD analyses will be performed based on correlation of plasma concentrations of C1 INH antigen (protein volume), functional C1 INH activity (potency), and C4 complement in conjunction with various safety parameters (eg, selected AEs, clinical laboratory results, antibodies generation; frequency, severity, or anatomic location of the HAE attack). Correlations that will be analyzed will be determined based on observed data.

Pharmacokinetic/pharmacodynamic parameters and PK/PD assessments will be summarized using descriptive statistics (number, mean, standard deviation, median, minimum, and maximum) and categorical parameters will be summarized using frequency statistics (number and percentage of subjects).

7.6 Efficacy Analyses

7.6.1 Prevention of Angioedema Attacks

The following efficacy endpoints for prevention of angioedema attacks will be assessed:

- The number of angioedema attacks recorded during the treatment period, normalized for the number of days the subject participated in the period.
- The overall frequency of angioedema attacks occurring during the treatment period will be calculated and compared with historical baseline values.
- Summary of all attacks during the treatment period, including:
 - Anatomic location.
 - Severity (intensity).
 - Duration.
 - Number of rescue treatments (including antiemetics, narcotics, or C1 INH therapy, including administration of rescue CINRYZE).
- Effects of therapy on quality of life (results of AE-QoL questionnaire).

7.6.2 Treatment of Breakthrough Angioedema Attacks

The following efficacy endpoints for treatment of breakthrough angioedema attacks will be assessed by CINRYZE-treated attack number:

- The number of subjects who achieve Clinical Relief. Clinical Relief is defined as a sustained reduction from pre-infusion in the attack severity within 4 hours after initiation of treatment with CINRYZE.
- Time to onset of Clinical Relief.
- The number of subjects who achieve Complete Resolution. Complete Resolution is defined as the cessation of all symptoms of the breakthrough angioedema attack.
- Time to Complete Resolution.

Other analyses may be performed to establish context of the efficacy results from this study with previous Phase 3 CINRYZE studies.

8 DRUG SUPPLIES

8.1 How Supplied

CINRYZE is supplied as a lyophilized powder in single use vials containing 500 U of C1 INH per vial. When reconstituted, CINRYZE contains C1 INH at a concentration of 100 U/mL in a citrate-buffered solution comprising sucrose, sodium chloride, L-valine, L-alanine, and L-threonine.

Vials must be stored at $2^{\circ}\text{C} - 25^{\circ}\text{C}$ ($36^{\circ}\text{F} - 77^{\circ}\text{F}$) and protected from light. Do not freeze.

8.1.1 For at Home Use

Subjects (or their caregivers) who elect to self-administer investigational product at home will be provided the following supplies at investigational site for transport to the home location:

- 4-week supply of investigational product, including sterile water for injection, and Mix2vial® transfer devices
- Ancillary supplies, including silicone-free syringes, needles, infusion sets, disinfecting strips, and disposal containers (eg, sharps and infectious materials)
- Transport container for investigational product
- Subject accountability log to record investigational product storage conditions, administration, and other details.

All used and unused vials of investigational product should be returned to the study site for inspection and drug accountability purposes.

8.2 Reconstitution of CINRYZE for Intravenous Infusion

Each vial of CINRYZE will be reconstituted with 5 mL of Sterile Water for Injection (SWFI). The following supplies will be required for reconstitution using aseptic technique: United States Pharmacopeia (USP) SWFI, disinfecting strips, Mix2Vial transfer device, and silicone-free disposable syringes.

For subjects 6 years of age and older, each 1000 U infusion will require reconstitution of two 500 U vials of CINRYZE; for subjects 2 to 5 years of age, each 500 U infusion will require reconstitution of one 500 U vial of CINRYZE. The solution must be used within 3 hours after reconstitution.

Instructions for the reconstitution of CINRYZE will be provided in separate study manual.

8.3 Drug Accountability

The Principal Investigator must maintain records of study drug product received, including dates of receipt, expiry and dispensing, in addition to lot numbers. Study personnel will enter each lot number of CINRYZE administered to a subject in the subject's CRF. In addition, records must be kept on when and how many study drug vials were dispensed and returned for each individual subject in the trial. Reasons for departure from the expected dosing regimen must also be

recorded in both source documents and the CRF. Sponsor representatives will review drug accountability on an ongoing basis throughout the study. An overall summary of all drug supplies received and used must be recorded on the appropriate forms and signed by the Principal Investigator and clinical monitor at the conclusion of the study. Written records will be maintained documenting a final accounting of study drug received at the investigational site and study drug vials dispensed to subjects. All unopened/unused/used study drug vials will be returned by the clinical research associate (CRA) to the central distributor or destroyed by the Investigator per local regulations or standard operating procedures (SOPs).

8.4 Drug Labels

Clinical trial labels that are in accordance with applicable regulatory requirements will be applied. The label will comply with Japanese GCP.

9 ADVERSE AND SERIOUS ADVERSE EVENTS ASSESSMENT

9.1 Definition of Adverse Events, Period of Observation, Recording of Adverse Events

An **AE** is any untoward medical occurrence in a clinical investigation subject administered a pharmaceutical product and that does not necessarily have a causal relationship with this treatment. An AE can therefore be any unfavorable and unintended sign (including an abnormal laboratory finding), symptom, or disease temporally associated with the use of a medicinal (investigational) product, whether or not related to the medicinal (investigational) product (ICH Guidance E2A 1995).

All AEs are collected from the time the informed consent is signed until the defined follow-up period stated in Section 3. This includes events occurring during the screening phase of the study, regardless of whether or not investigational product is administered. Where possible, a diagnosis rather than a list of symptoms should be recorded. If a diagnosis has not been made, then each symptom should be listed individually. All AEs should be captured on the appropriate AE pages in the CRF and in source documents. In addition to untoward AEs, unexpected benefits outside the investigational product indication should also be captured on the AE CRF.

All AEs must be followed to closure (the subject's health has returned to his/her baseline status or all variables have returned to normal), regardless of whether the subject is still participating in the study. Closure indicates that an outcome is reached, stabilization achieved (the Investigator does not expect any further improvement or worsening of the event), or the event is otherwise explained. When appropriate, medical tests and examinations are performed so that resolution of event(s) can be documented.

9.1.1 Severity Categorization

The severity (intensity) of AEs will be assessed according to the definitions below. If the intensity of an AE changes over time, the maximum intensity experienced should be recorded.

Mild: A type of AE that is usually transient and may require only minimal treatment or

therapeutic intervention. The event does not generally interfere with usual

activities of daily living.

Moderate: A type of AE that is usually alleviated with specific therapeutic intervention. The

event interferes with usual activities of daily living, causing discomfort but poses

no significant or permanent risk of harm to the research subject.

Severe: A type of AE that interrupts usual activities of daily living, or significantly affects

clinical status, or may require intensive therapeutic intervention.

Worsening of pre-treatment events, after initiation of investigational product, must be recorded as new AEs (for example, if a subject experiences mild intermittent dyspepsia prior to dosing of investigational product, but the dyspepsia becomes severe and more frequent after first dose of investigational product has been administered, a new AE of severe dyspepsia [with the appropriate date of onset] is recorded on the appropriate CRF).

9.1.2 Relationship Categorization

A physician/Investigator must make the assessment of relationship to investigational product for each AE. The Investigator should decide whether, in his or her medical judgment, there is a reasonable possibility that the event may have been caused by the investigational product. If there is no valid reason for suggesting a relationship, then the AE should be classified as "not related." Otherwise, if there is any valid reason, even if undetermined or untested, for suspecting a possible cause-and-effect relationship between the investigational product and the occurrence of the AE, then the AE should be considered "related." The causality assessment must be documented in the source document.

The following additional guidance may be helpful:

| Term | Relationship Definition |
|-------------|---|
| Related | The temporal relationship between the event and the administration of the investigational product is compelling and/or follows a known or suspected response pattern to that product, and the event cannot be explained by the subject's medical condition, other therapies, or accident. |
| | |
| Not Related | The event can be readily explained by other factors such as the subject's underlying medical condition, concomitant therapy, or accident and no plausible temporal or biologic relationship exists between the investigational product and the event. |

9.1.3 Outcome Categorization

The outcome of AEs must be recorded during the course of the study on the CRF. Outcomes are as follows:

- Fatal
- Not Recovered/Not Resolved
- Recovered/Resolved
- Recovered/Resolved With Sequelae
- Recovering/Resolving
- Unknown.

9.1.4 Symptoms of the Disease Under Study

In this study, angioedema attacks will not be reported as adverse events unless the attack meets the definition of a serious adverse event (see Section 9.2.3).

9.1.5 Clinical Laboratory and Other Safety Endpoints

A change in the value of a clinical laboratory, vital sign, or ECG assessment can represent an AE if the change is clinically relevant or if, during treatment with the investigational product, a shift of a parameter is observed from a normal value to an abnormal value, or a further worsening of an already abnormal value. When evaluating such changes, the extent of deviation from the reference range, the duration until return to the reference range, either while continuing treatment

Protocol 0624-209 with Amendments 1, 2, 3 CINRYZE (C1 inhibitor [human])

or after the end of treatment with the investigational product, and the range of variation of the respective parameter within its reference range, must be taken into consideration.

If, at the end of the treatment phase, there are abnormal clinical laboratory, vital sign, or ECG values which were not present at the pre-treatment value observed closest to the start of study treatment, further investigations should be performed until the values return to within the reference range or until a plausible explanation (eg, concomitant disease) is found for the abnormal values.

The Investigator should decide, based on the above criteria and the clinical condition of a subject, whether a change in a clinical laboratory, vital sign, or ECG parameter is clinically significant and therefore represents an AE.

9.1.6 Pregnancy

All pregnancies are to be reported from the time informed consent is signed until the defined follow-up period stated in Section 3.

Any report of pregnancy for any female study participant or the female partner of a male study participant must be reported within 24 hours to PAREXEL International Pharmacovigilance using the Shire Investigational and Marketed Products Pregnancy Report Form. The pregnant female study participant must be withdrawn from the study.

Every effort should be made to gather information regarding the pregnancy outcome and condition of the infant. It is the responsibility of the Investigator to obtain this information within 30 calendar days after the initial notification and approximately 30 calendar days postpartum.

Pregnancy complications such as spontaneous abortion/miscarriage or congenital abnormality are considered SAEs and must be reported using the Shire Clinical Trial Serious Adverse Event Form. **NOTE:** An elective abortion is not considered an SAE.

In addition to the above, if the Investigator determines that the pregnancy meets serious criteria, it must be reported as an SAE using the Shire Clinical Trial Serious Adverse Event Form as well as the Shire Investigational and Marketed Products Pregnancy Report Form. The test date of the first positive serum/urine β -HCG test or ultrasound result will determine the pregnancy onset date.

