Throughout the trial, a study diary will be used by subjects (or caregivers) to record specific information about any angioedema attack symptoms and details on the self-administration of investigational product (see Section 6.11). Because of the potential to precipitate an angioedema attack, subjects will be requested to postpone elective medical procedures (eg, dental work) and avoid other known attack triggers while participating in the study (see Section 6.10).

Safety will be assessed by monitoring adverse events and changes in physical examinations, vital signs, and clinical safety laboratory testing. In addition, subjects will be monitored for the development of antibodies to C1 INH. If clinically indicated, study personnel may perform examinations to actively monitor subjects for possible venous thromboembolism or other thrombotic or thromboembolic (T/TE) events. Stopping rules are provided in Section 5.5.

Protocol 0624-209 with Amendments 1, 2, 3, 4, and CINRYZE (C1 inhibitor [human])

In this study, angioedema attacks will not be reported as adverse events unless the attack meets the definition of a serious adverse event (see Section 9.1.4).

Adverse events will be recorded from the time the informed consent is signed through 7 days after the last dose of investigational product. This includes events occurring during the screening phase of the study, regardless of whether or not the investigational product is administered. In addition, the investigator will report all SAEs that occur through 30 days after the last dose of investigational product to PAREXEL International Pharmacovigilance and the respective Independent Reviewing Authority according to local reporting requirements.

Post-treatment follow-up visits will be performed 1 week (± 1 day) and 1 month (30 ± 2 days) after the last dose of study drug. If a subject prematurely discontinues investigational product, regardless of the reason, the Early Discontinuation Visit procedures listed in Schedule 3 are to be performed as completely as possible. Whenever possible, all discontinued subjects should also complete the 1-Week and 1-Month Post-treatment Follow-up visits.

The schedules of study procedures are provided as follows:

- Schedule 1: Clinical Study Assessments Screening and Treatment Period;
- Schedule 2: Investigational Product and Self-administration Training;

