4.1 Inclusion Criteria

To be eligible for this protocol, a subject must:

- 1. Be of Japanese descent, defined as born in Japan and having Japanese parents and Japanese maternal and paternal grandparents.
- 2. Be ≥ 2 years of age.
- 3. Meet the following minimum body weight criteria:
 - Subjects 2 to 5 years of age must weigh at least 12.5 kg; and
 - Subjects 6 years of age and above must weigh at least 25 kg.
- 4. Have a confirmed diagnosis of Type I or Type II HAE. **NOTE:** Diagnosis may be based on historical data including family history, clinical symptoms (characteristic attacks), and documentation of low level of C1 INH protein and/or C1 INH activity.
- 5. Have a history of at least one angioedema attack per month (on average) during the 3 consecutive months immediately before enrollment.
- 6. Agree to adhere to the protocol-defined schedule of assessments and procedures.
- 7. Agree to avoid his/her known angioedema attack triggers during the study to the best of his/her ability.
- 8. If a female of reproductive age, be postmenopausal (≥12 months following cessation of menstruation), surgically sterile, or following an acceptable method of birth control (and agree to continue its use through 1 month after the last dose of study drug):
 - Non-hormonal methods (eg, abstinence, barrier control) for at least 1 complete menstrual cycle before the Screening Visit.
 - Stable doses of estrogen and/or progestin containing products for at least 2 months before the Screening Visit.
- 9. If a male of reproductive age, be surgically sterile or agree to follow an acceptable method of birth control (eg, abstinence, barrier control) from the Screening Visit through 2 months after the last dose of study drug.
- 10. If an adult, be informed of the nature of the study and provide written informed consent before any study-specific procedures are performed.

OR

If a child or minor (<20 years of age), have a parent/legal guardian who is informed of the nature of the study provide written informed consent (ie, permission) for the child to

Protocol 0624-209 with Amendments 1, 2, 3, 4, and 5 CINRYZE (C1 inhibitor [human])

participate in the study before any study-specific procedures are performed. Assent will be obtained from children ≥14 years of age.

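### Protocol Section 9.1.6 does not define the pregnancy reporting period, and no reading of its Section 3 reference reaches the 2 months of contraception required of male subjects

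*Protocol*

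**What the plan says.** Protocol Section 9.1.6 sets the reporting period by cross-reference only: "All pregnancies are to be reported from the time informed consent is signed until the defined follow-up period stated in Section 3". Its next paragraph sets the speed of reporting and brings partners into scope: "Any report of pregnancy for any female study participant or the female partner of a male study participant must be reported within 24 hours". That sentence carries no end date.

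The text of Section 3 does not mention pregnancy. It offers three candidate endpoints:

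- Adverse events: "Adverse events will be recorded from the time the informed consent is signed through 7 days after the last dose of investigational product".
- Serious adverse events: "the investigator will report all SAEs that occur through 30 days after the last dose of investigational product".
- Visits: "Post-treatment follow-up visits will be performed 1 week (± 1 day) and 1 month (30 ± 2 days) after the last dose of study drug".

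Section 9.1 points to Section 3 in the same terms for adverse events: "All AEs are collected from the time the informed consent is signed until the defined follow-up period stated in Section 3". There the reference leads to 7 days.

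The contraception periods are in Section 4.1. Under criterion 8, female subjects must "agree to continue its use through 1 month after the last dose of study drug". Under criterion 9, male subjects who are not surgically sterile must agree to an acceptable method "from the Screening Visit through 2 months after the last dose of study drug".

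Pregnancy tests for women of childbearing potential are scheduled at Screening, Dosing Visit 1 and Dosing Visit 24 (Schedule 1, with sampling before the infusion under note c), and at the Early Discontinuation Visit (Schedule 3). Schedule 3 has none at the 1-Week or 1-Month visit.

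**The concern.** A site that follows Section 9.1.6 must first decide which Section 3 period applies, and sites may decide differently. Whichever they choose, the stated period for reporting partner pregnancies ends well before the period for which the protocol asks male subjects to prevent conception.

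The consequence is a loss of safety information. Section 9.1.6 times the collection of pregnancy outcome and infant condition from the initial notification, so a pregnancy that is never notified starts no follow-up. Section 1.1.1 makes that information worth having. The rat organogenesis work showed no fetal harm, but an antibody-mediated effect could not be excluded, and no specific fertility, early embryonic or postnatal studies were done.

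Two features add to the problem. Section 9.1.6 dates the onset of a pregnancy by the first positive test or ultrasound. A conception during treatment that is first confirmed on, say, day 40 after the last dose therefore has an onset date beyond both the 7-day and the 30-day period. And completers have no scheduled test after the last planned dose that would bring such a pregnancy to light sooner.

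**Working it through.** The plan states no figure to reproduce. The check is day arithmetic.

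**Inputs**

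- Reporting end R, in days after the last dose (Section 3): 7 (adverse events), 30 (serious adverse events), or 28 to 32 (1-Month visit window).
- Contraception period C (Section 4.1): 1 month for female subjects, 2 months for male subjects.
- Assumption: 1 month = 30 days (range 28 to 31) and 2 months = 60 days (range 59 to 62). The protocol fixes a month at 30 ± 2 days for the visit only.

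**Formula:** uncovered days = max(0, C − R); share = uncovered days / C.

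| Subjects | R | Uncovered days (C = 60 or 30) | Share | Range over month lengths |
|---|---|---|---|---|
| Male (partners) | 30 | 60 − 30 = 30 | 50% | 59 − 30 = 29 to 62 − 30 = 32 |
| Male (partners) | 28 to 32 (visit) | 60 − 32 = 28 to 60 − 28 = 32 | 47% to 53% | 59 − 32 = 27 to 62 − 28 = 34 |
| Male (partners) | 7 | 60 − 7 = 53 | 88% | 59 − 7 = 52 to 62 − 7 = 55 |
| Female | 30 | 30 − 30 = 0 | 0% | 0 to 31 − 30 = 1 |
| Female | 28 to 32 (visit) | 0 to 30 − 28 = 2 | 0% to 7% | 0 to 31 − 28 = 3 |
| Female | 7 | 30 − 7 = 23 | 77% | 28 − 7 = 21 to 31 − 7 = 24 |

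The male shortfall is never below 27 days under any reading or month length. The female shortfall is 0 to 3 days unless the 7-day period is meant.

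**Detection.** For a completer, the last scheduled test is before the Visit 24 infusion, so no scheduled test falls after the last dose. Section 6.12.1 also allows a supplemental dose through 1 week post-treatment, so the last test can precede the actual last dose by about a week.

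**Effect of the fix.** With R set equal to C for each sex, the uncovered days are 0 by construction.

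**The case against.** Several points on the other side are fair and limit what can be claimed.

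- **Pregnancies are not shown to be lost.** A reader might infer that in-window pregnancies are missed, or that a day-45 partner pregnancy is not reportable. The 24-hour sentence in Section 9.1.6 has no end date, and an investigator who hears of such a pregnancy could reasonably report it. But that sentence sets how fast to report, while the one before it sets the period. The supportable claim is that a report can be missed.
- **The largest figures depend on one reading.** The 53 of 60 and 23 of 30 days assume the 7-day period. Section 9.1 gives that reading some support. In Section 3, however, the term follow-up is attached to the post-treatment visits, the last of them at 30 ± 2 days. The 7-day figures are a possible upper case, not the finding.
- **A conception is not in itself a breach.** Criterion 9 asks for sterility or agreement to use a method. A pregnancy despite correct use is a method failure.
- **The protocol does not call these risk windows.** The contraception periods are eligibility criteria. Section 1.1.2 gives half-lives of about 60 hours (functional activity) and 45 to 47 hours (antigen). At 60 hours, day 30 is 720 / 60 = 12 half-lives and day 45 is 1080 / 60 = 18. Little residual drug would be expected. This lowers the clinical weight of the gap but does not remove the inconsistency between the two sections.
- **Partial backstops exist.** Section 9.1.6 classes miscarriage and congenital abnormality as serious adverse events, Section 9.2.4 keeps related serious events reportable after the study, and Schedule 3 collects events at the 1-Month visit. None of these covers an uncomplicated pregnancy that comes to light later.
- **An added test would not close the female window.** A single test at day 30 ± 2 cannot reliably detect a conception in the days just before it. It would help mainly with conceptions late in treatment, and no section requires it.

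**Conclusion.** The point holds for partners of male subjects under every reading. Section 9.1.6 does not say which Section 3 period governs pregnancy, and the longest on offer ends about 30 days before the 2 months in criterion 9. The shortfall is 53 of 60 days if the 7-day period is meant.

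For female subjects there is no material reporting gap on the 30-day reading. A gap of about 23 of 30 days exists only on the 7-day reading. The absence of a scheduled test after the last dose in completers is a separate limit on detection, not a reporting error.

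These figures rest on 30-day months and count calendar days. They are not expected numbers of pregnancies: the plan gives no conception rate or sex mix, and the target is a minimum of 6 completers. Few events, possibly none, would be affected. Efficacy and pharmacokinetic analyses are untouched. This is a safety-reporting inconsistency that should be corrected because the remedy is specific and cheap.

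**What to change.** In Section 9.1.6, replace the reference to Section 3 with an explicit reporting period reconciled with criteria 8 and 9 of Section 4.1:

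- from consent through 1 month after the last dose for female subjects;
- from consent through 2 months after the last dose for partners of male subjects;
- in both cases including a pregnancy discovered later but conceived within that period, so that the test-based onset date does not exclude it.

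Instruct male subjects to notify the site of a partner pregnancy in that time.

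The cost is protocol wording, one instruction to male subjects, and slightly longer passive safety reporting. No visit, dose or analysis changes.

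Whether to add the site-standard pregnancy test to the existing 1-Month visit, where blood is already drawn for antibody testing, is an optional monitoring choice for the sponsor. It is not part of the required correction.
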